## **6.3 Measures to Minimize Bias: Randomization and Blinding**

On Day 1, Participants will be assigned a unique number (randomization number) in ascending numerical order. The randomization number encodes the Participant's assignment to study treatment according to the randomization schedule generated prior to the study by the Statistics Department of █████. This is a double-blind study with limited access to the randomization code. OP0201 and placebo will be identical in physical appearance. The specific treatment each Participant will receive (OP0201 or placebo) will not be disclosed to the Investigator, study

center staff, Participant, Sponsor, study vendors, or the Safety Monitoring Committee (SMC). The treatment codes will be held by the Clinical Supplies Department of the Sponsor.

Participants will be randomly allocated in a 1:1 ratio to receive OP0201 or placebo as adjunct treatment to 20 doses of protocol defined oral antibiotic treatment.

Randomization will be stratified by daycare attendance (yes, no) and age ( $\geq 6$  to  $<12$  months,  $\geq 12$  to  $\leq 24$  months). Daycare attendance “yes” is defined as exposure to 3 or more children outside of the home for 10 or more hours per week.

## **6.4 Study Treatment Compliance**

The prescribed dosage, timing, and mode of administration may not be changed. Any deviations from the protocol defined study treatment regimen must be recorded in the eCRFs.

Parents/caregivers of Participants will be issued a study diary in which they will be instructed to record daily the date and time of study treatment and antibiotic administration. If a study treatment or antibiotic dose is missed or a partial dose is given, this should also be recorded, and the dosing should resume at the next scheduled time.

At the Day 4 Visit and the Day 12 Visit, previously dispensed study treatment and the diary will be retrieved by the Investigator and compliance assessed. Parents/caregivers exhibiting poor compliance as assessed by diary completion should be counseled on the importance of good compliance to the study dosing regimen.

## **6.5 Concomitant Therapy**

Any medication or vaccine (including over-the-counter or prescription medicines, vitamins, and/or herbal supplements) that the Participant has received within the 7 days before enrollment (prior therapy) or receives during the study period and after first dose of study treatment (concomitant therapy) must be recorded on the eCRF along with:

- Reason for use.
- Date of administration including start and end date.
- Dosage information including dose, route, and frequency.

The Medical Monitor should be contacted if there are any questions regarding concomitant or prior therapy.

### **6.5.1 Excluded Medications**

Participants must abstain from taking antimicrobial therapy within the 3 days (ie, 72 hours) prior to Day 1. Excluded medications/therapy is listed below:

- Any intranasal treatments other than saline rinse.

- Any systemic or locally administered drug containing phenylephrine.

The use of an excluded medication/therapy is a protocol violation and must be recorded in the eCRF.

#### **6.5.2 Other Concomitant Medications**

Other concomitant medication may be considered on a case-by-case basis by the Investigator in consultation with the Medical Monitor, if required for the wellbeing of the Participant.

#### **6.6 Dose Modification**

Dose modifications are not planned in this study.

#### **6.7 Treatment After the End of the Study**

The Sponsor will not provide any additional care to Participants after they leave the study.

## **7.0 DISCONTINUATION OF STUDY TREATMENT AND PARTICIPANT DISCONTINUATION/WITHDRAWAL**

If a clinically significant finding is identified, the Investigator or qualified designee will determine if the Participant should continue with the study treatment and if any change in Participant management is needed, and/or if they should remain in the study. Any new clinically relevant finding should be reported as an AE.

### **7.1 Discontinuation of Study Treatment**

The Investigator may use their discretion in deciding whether to discontinue the Participant from the study. If the Participant is discontinued from the study early, see [Table 3](#) for data to be collected at the time of study discontinuation. The reason that the study treatment is stopped should be documented on the appropriate eCRF.

### **7.2 Participant Discontinuation/Withdrawal from the Study**

Participants who meet any of the following criteria should not receive further study treatment and should be exited from the study. See [Table 3](#) for data to be collected at the time of Study Exit.

- Investigator or Sponsor (or its designee) decides to discontinue Participants from the study for safety, behavioral, compliance, or administrative reasons.
- Parent/legal guardian of Participant indicates that they no longer want the Participant to participate in the study. If the parent/legal guardian of the Participant withdraws consent for disclosure of future information, the Sponsor may retain and continue to use any data collected before such a withdrawal of consent.

Notification of early Participant withdrawal from the study and the reason for discontinuation will be clearly documented and noted in the eCRF. If the Participant exits the study prior to the Day 28 Study Exit visit, all of the Day 28 final measurements should be performed and recorded on the appropriate eCRF.

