#### **4.6 Study Stopping Criteria**

##### **4.6.1 Stopping Criteria for Individual Participants**

Study treatment for any individual Participant will be stopped if the Participant experiences an SAE or a clinically significant possibly study treatment-related AE, which in the opinion of the Principal Investigator, Medical Safety Physician and Sponsor's medical representative, warrants discontinuation of the study for that Participant's wellbeing.

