#### **8.4.6.2 Follow-up of Medical Device Incidents**

- All Medical Device Incidents involving an AE will be followed and reported in the same manner as other AEs (see [Appendix 3](#)). This applies to all Participants, including those who discontinue study treatment.
- The Investigator is responsible for ensuring that follow-up includes any supplemental investigations as indicated to elucidate the nature and/or causality of the incident.
- New or updated information will be recorded on the originally completed form with all changes signed and dated by the Investigator.

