9.1 Subject Disposition

Frequencies and percentages of subjects who discontinued the study treatment and/or study will be summarized. Reasons for discontinuation will also be summarized. The listing of subject disposition will include dates and times (if applicable) of randomization, dosing, and EOS; and reasons for study treatment and/or study discontinuation (if applicable).

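### Follow-up after study treatment stops is not secured, and exit for poor compliance is permitted, so Day 12 outcomes in particular may be missing for reasons related to prognosis

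*Protocol*

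**What the plan says.** **Leaving the study.** Protocol 7.2 states: "Participants who meet any of the following criteria should not receive further study treatment and should be exited from the study". One of its two grounds is that the investigator or sponsor "decides to discontinue Participants from the study for safety, behavioral, compliance, or administrative reasons". The other is that the parent or guardian no longer wants the child to take part. Early leavers have the Day 28 measurements, otoscopy included, done at departure.

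**Stopping treatment.** Protocol 7.1 carries this title, but its text concerns leaving the study: "The Investigator may use their discretion in deciding whether to discontinue the Participant from the study". Protocol 4.6.1 stops treatment for an adverse event that "warrants discontinuation of the study for that Participant's wellbeing".

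**Text that separates the two.** Protocol 7.0 says of the investigator or a delegate, after a clinically significant finding: "will determine if the Participant should continue with the study treatment and if any change in Participant management is needed, and/or if they should remain". Its last words concern study participation, as distinct from treatment. Protocol 8.4.6.2, on device incidents involving an adverse event, says: "This applies to all Participants, including those who discontinue study treatment". SAP 9.1 says: "Frequencies and percentages of subjects who discontinued the study treatment and/or study will be summarized".

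**Poor compliance.** Protocol 6.4 provides for counselling and does not mention exit.

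**Analysis.** SAP 7 analyses the primary (mITT) population by randomized assignment, whatever treatment was received. SAP 8.7 accepts otoscopy on study days 4–6 for Day 4 and 12–14 for Day 12, and excludes observations that fall in no window. SAP 13.3 imputes missing primary outcomes from the observed response rate in the child's own arm, with treatment group as the only predictor. SAP 16 records that this replaces the protocol's rule that missing counts as failure.

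**The concern.** A comparison by randomized assignment needs each child's outcome whether or not treatment continued. Where the protocol permits exit for poor compliance, or leaves it unclear whether an off-treatment child stays, an outcome that could have been observed may become missing. Children who stop treatment or comply poorly may also differ in prognosis from those who stay.

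Day 12 is the more exposed endpoint. A child who leaves after the Day 4 visit already has the Day 4 result, but an exit examination on, say, Day 8 falls in no window and cannot serve for Day 12.

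The SAP's imputation gives such a child the response rate of those who stayed in the same arm. The sensitivity analyses in SAP 12.1 and 12.2 are per-protocol, complete-case, and complete-case with no recurrence. None of them supposes that leavers did worse, and missing-as-failure is not kept even as a sensitivity analysis. An outcome-related pattern of exits would therefore not be tested by any planned analysis.

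**Working it through.** **1. The sections side by side**

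- Stopping treatment and leaving the study are linked in 4.6.1 and blurred in 7.1. They are separate in 7.0, 8.4.6.2 and SAP 9.1.
- The opening sentence of 7.2 runs from study exit to stopping treatment. It does not say that a child who stops treatment must exit.
- Compliance leads to counselling in 6.4 and is a permitted ground for exit in 7.2.

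**2. The plan's own use of dropout: power**

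Inputs (Protocol 9.2, SAP 5): 70 per arm; placebo rates 0.40 (Day 4) and 0.30 (Day 12); difference 0.25, so active rates 0.65 and 0.55; Hochberg at 0.05/0.025. Endpoints are taken as independent (an assumption).

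Power for at least one endpoint = a1 + a2 − a1·a2 + (b1 − a1)(b2 − a2), where a and b are the single-endpoint powers at 0.025 and 0.05.

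- Protocol (12% dropouts counted as failures, so all rates × 0.88): a = 0.647 and 0.677; b = 0.748 and 0.773. Result: 0.647 + 0.677 − 0.438 + 0.101 × 0.096 = 0.896. Simulation of the Pearson test gives 88.3%, within 2 points of the stated 87%.
- SAP (10% dropout, 63 per arm): 93.3%, against 93% stated.
- No missing data: 95.6% if the full effect is kept. If 10% or 12% of the active arm stay but respond at the placebo rate, 90.4% or 88.9%.

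The stated power is not in dispute, and better retention need not raise it. The reason for the fix is the validity of the comparison.

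**3. Possible bias at Day 12**

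The documents give no missing rates by arm and no outcomes for leavers, so d and m below are assumptions. Within-arm imputation is approximated by the complete-case comparison, since it draws from the same observed rate.

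Observed rate = (p − d·m)/(1 − d), with p the true rate in all children, d the fraction missing and m the response rate among those missing. Here p = 0.30 in both arms (no treatment effect). Example: 0.30/0.88 = 0.341; 0.30/0.95 = 0.316; difference 0.025. The last column is the rejection rate of a single two-sided test at 0.05.

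| Missing, OP0201 v placebo | m | Observed rates | Bias (points) | Rejection |
|---|---|---|---|---|
| 12% v 12% | 0 | 0.341, 0.341 | 0 | 5.0% |
| 12% v 5% | 0 | 0.341, 0.316 | +2.5 | 6.1% |
| 15% v 5% | 0 | 0.353, 0.316 | +3.7 | 7.3% |
| 20% v 5% | 0 | 0.375, 0.316 | +5.9 | 10.6% |
| 15% v 5% | 0.15 | 0.326, 0.308 | +1.9 | 5.6% |
| 15% v 5% | 0.30 | 0.300, 0.300 | 0 | 5.0% |

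The sign reverses if placebo loses more children. Under the protocol's missing-as-failure rule, the bias in the unequal cases is −(d_OP0201 − d_placebo)·m, at most in size −(0.20 − 0.05) × 0.30 = −4.5 points and never in favour of OP0201.

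If the treatment works (0.55 v 0.30), equal missingness no longer cancels. At 10% missing in each arm, all failing, 0.611 − 0.333 = 0.278, which overstates the difference by 2.8 points.

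**The case against.** The strongest case against is that the protocol does let an off-treatment child stay. Section 7.0 makes treatment and study continuation separate decisions, 7.1 leaves exit to discretion, and 8.4.6.2 and SAP 9.1 recognise children who stop treatment only. Table 3 schedules otoscopy at Days 4, 12 and 28 with no on-treatment condition, and Section 8.0 makes adherence to Table 3 a requirement. Additional antibiotics for treatment failure are not an exit ground. Exit for compliance is permitted, not automatic, and the decisions are blinded, which makes a difference between arms less likely.

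All of this stands, and it rules out two stronger readings. A reader might infer that the protocol gives no route to stay after treatment stops; 7.0 contradicts that. A reader might take the opening of 7.2 to mean that stopping treatment forces exit; it says the converse.

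A reader might also multiply missing share by arm rate at Day 4, for example 0.15 × 0.65 − 0.05 × 0.40 = 7.75 points, and treat that as the size of the defect. The documents do not support this. It attributes all dropout to these sections, although the allowance also covers parental withdrawal and loss to follow-up. It uses the less exposed endpoint, assumes an uneven split and needs every leaver to fail.

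The objection does not remove the gap. The schedule binds a child who remains in the study, but nothing says that a child who stops treatment remains. Section 4.6.1 points the other way, and 7.2 still permits exit for compliance.

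**Conclusion.** The point holds as a gap in the rules that may produce avoidable missing primary outcomes, mainly at Day 12, possibly related to prognosis. It does not show that informative missingness will occur. With no true effect, bias needs missingness that both depends on outcome and differs between arms. In the scenarios shown for Day 12 with leavers all failing, it ranges from 0 (12% in each arm) through +2.5 (12% v 5%) and +3.7 (15% v 5%) to +5.9 points (20% v 5%). It is 0 when leavers respond like stayers. Those missing rates and outcomes are assumptions, and the share of dropout that comes from compliance or off-treatment exits is unknown. The SAP's imputation makes the gap matter more than the protocol's missing-as-failure rule did. This is an inexpensive improvement; it does not undermine the design.

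**What to change.** Reconcile Protocol 4.6.1, 6.4, 7.0, 7.1 and 7.2 on whether stopping treatment means leaving the study. In 7.1 and 7.2, state that stopping study treatment does not by itself end participation, and that such children are still asked to attend the scheduled Day 4, 12 and 28 outcome visits unless consent is withdrawn. Remove compliance as a ground for study exit. Leave the safety and administrative exit grounds, and every rule on when treatment is stopped, as they are.

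The cost is a short amendment. The visits are already in Table 3 for every child. The small downside is that some families will decline them, so some missing data will remain.

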### **7.3 Lost to Follow-up**

A Participant will be considered lost to follow-up if he or she fails to return for scheduled visits and is unable to be contacted by the study center.

The following actions must be taken if a Participant fails to return to the study center for a required study visit:

- The study center must attempt to contact the parent/caregiver of the Participant and reschedule the missed visit as soon as possible and counsel the parent/caregiver of the

Participant on the importance of maintaining the assigned visit schedule and ascertain whether or not he/she wishes the Participant to continue in the study.

- Before a Participant is deemed lost to follow-up, the Investigator or designee must make every effort to regain contact with the parent/caregiver of the Participant (where possible, 3 telephone calls and, if necessary, a certified letter to the Participant's last known mailing address or local equivalent methods). These contact attempts should be documented in the Participant's medical record.
- Should the Participant continue to be unreachable, he/she will be considered to have withdrawn from the study and not returning for scheduled visits.

## 8.0 STUDY ASSESSMENTS AND PROCEDURES

This section provides a high-level summary of the study assessments to be performed. For details as to when these assessments are performed see [Table 3](#).

- Study procedures and their timing are summarized in [Table 3](#).
- Protocol waivers or exemptions are not allowed.
- Safety concerns should be discussed with the Sponsor immediately upon occurrence or awareness to determine if the Participant should continue or discontinue study treatment.
- Adherence to the study design requirements, including those specified in [Table 3](#), is essential and required for study conduct.
- All screening evaluations must be completed and reviewed to confirm that potential Participants meet all eligibility criteria. The Investigator will maintain a screening log to record details of all Participants screened and to confirm eligibility or record reasons for screening failure, as applicable.
- Procedures conducted as part of the Participant's routine clinical management (eg, audiology hearing test) and obtained before signing of the informed consent form (ICF) may be utilized for screening or baseline purposes provided the procedures meet the protocol-specified criteria and were performed within the time frame defined in [Table 3](#).

### 8.1 Efficacy Assessments

Pneumatic otoscopy\* to evaluate each TM for:

- TM: intact, perforated
- Color (check all that apply): gray, pink, pale yellow, white, amber, blue
- Translucency: translucent, opaque, semi-opaque
- Mobility: none, 1+, 2+, 3+, 4+
- Air fluid interface: yes, no
- Distinct erythema: yes, no
- Position: neutral, retracted, 1+ bulging, 2+ bulging, 3+ bulging
- Otorrhea: no, serous, purulent

\*Note: Trained otoscopists who have undergone comprehensive educational program (ePROM, enhancing proficiency in otitis media) for training in the diagnosis of AOM will perform the otoscopy assessments in this study. This training includes training on cerumen removal, which is required (as needed) prior to performing pneumatic otoscopy.

Tympanometry will be performed, when possible, to assess middle ear function (ie, TM mobility, ET function) by measuring the amount of sound energy reflected back when a small probe is placed in each ear canal. The output of the right ear and left ear tympanometry will be a

tympanogram tracing recorded using a 226 Hz probe tone and a positive (+300 decaPascals [daPa]) to negative (-600 daPa) air-pressure sweep at fast speed. Each tympanogram will be classified as Type A (normal), Type B (abnormal), or Type C (abnormal).

AOM-SOS score will be recorded daily by parent/caregiver during the 10-day course of study treatment and antibiotics, and recorded in-clinic at Day 4, Day 12, and Day 28.

## **8.2 Safety Assessments**

Planned time points for all safety assessments are provided in [Table 3](#).

### **8.2.1 Physical Examinations**

- A complete physical examination will be performed to assess any physical abnormalities and will include, at a minimum, assessment of the following body systems: overall status of the skin, head, neck, trunk, eyes, ears, heart, and lungs (eg, breathing sounds), abdomen, extremities, and lymph nodes.
- Physical examination will also include visual examination of the nasopharynx and oropharynx using a light source (for local effects).
- Height and weight will be measured and recorded on Day 1.
- Investigators should pay special attention to clinical signs related to previous serious illnesses.

### **8.2.2 Vital Signs**

- Temperature (as Celsius or Fahrenheit degrees) will be assessed and method obtained recorded.
- Respiration rate (per minute) will be measured by counting at least 30 seconds and multiplying accordingly.
- Pulse rate (beats/minute) will be assessed after the Participant has been at rest (seated) for approximately 5 minutes in a quiet setting without distractions with a completely automated device. Manual techniques will be used only if an automated device is not available. A total of 1 pulse reading should be recorded.

### **8.2.3 Otoscopy**

Pneumatic otoscopy and an endoscope-iPhone application that captures a video segment will be performed to assess the appearance of the TM.

### **8.2.4 Acute Otitis Media Symptom Burden**

Parents/caregivers will record the AOM symptom burden daily during the 10-day course of study treatment and antibiotics using the 5-question version of the AOM-SOS Scale. Each of the following 5 questions will be rated on a 6-point Likert scale (0 [no], 1 [almost none], 2 [a little], 3 [some], 4 [a lot], and 5 [an extreme amount]) (total score ranges from 0 to 25): (1) Over the past 12 hours, has your child been tugging, rubbing, or holding the ear(s) more than usual?;

(2) Over the past 12 hours, has your child been crying more than usual?, (3) Over the past 12 hours, has your child been more irritable or fussy than usual?, (4) Over the past 12 hours, has your child been having more difficulty sleeping than usual?, (5) Over the past 12 hours, has your child been having fever or feeling warm to touch?

### **8.3 Other Assessments**

1. Otalgia (per Investigator judgment in consultation with parent/caregiver): yes, no. Information used by the Investigator to confirm diagnosis. Data will be collected in the eCRF and summarized.
2. Endoscopic examination with image capture of each ear when possible, using an endoscope iPhone application (Pitt CMU iTM). Information used by the Investigator to confirm agreement of findings with Sub-investigators. Data will not be collected in the eCRF or analyzed.
3. Parent/caregiver's input on Device Experience Questionnaire. Data will be collected in the eCRF and summarized in data listings.

### **8.4 Adverse Events**

The definitions of an AE or SAE can be found in [Appendix 3](#).

Adverse events will be reported by the parent/caregiver of the Participant.

The Investigator and any designees are responsible for detecting, documenting, and recording events that meet the definition of an AE or SAE and remain responsible for following up AEs that are serious, considered related to the study treatment or study procedures, or that caused the Participant to discontinue the study treatment or study (see Section [7.0](#)).

#### **8.4.1 Time Period and Frequency for Collecting AE and SAE Information**

All SAEs will be collected from the time of signed informed consent obtained until the Study Exit.

All AEs will be collected from the time of signed informed consent obtained until the Study Exit.

Medical occurrences that begin before the start of study treatment but after obtaining signed informed consent will be recorded as pretreatment-emergent AEs in the AE section of the eCRF.

All SAEs will be recorded and reported to the Sponsor or designee within 24 hours, as indicated in [Appendix 3](#). The Investigator will submit any updated SAE data to the Sponsor within 24 hours of it being available.

Investigators are not obligated to actively seek AEs or SAEs after conclusion of the study participation. However, if the Investigator learns of any SAE, including a death, within 30 days of Study Exit, and he/she considers the event to be reasonably related to the study treatment or study participation, the Investigator must promptly notify the Sponsor.

The method of recording, evaluating, and assessing causality of AE and SAE and the procedures for completing and transmitting SAE reports are provided in [Appendix 3](#).

